4. STUDY DESIGN

4.1 Overall Design

This will be a single arm, Phase II study designed to evaluate the clinical activity of olaparib in mCRPC patients with evidence of HRR deficiency as determined using iHRD signature analysis. Patients will initially be screened for eligibility on the basis of a loss of heterozygosity (LOH) score optimized for UW OncoPlex, a clinical grade targeted sequencing assay. Eligible LOH score positive subjects will then enroll and receive treatment with olaparib 300 mg by mouth twice daily. One treatment cycle will be defined as 28-days, and consist of continuous daily dosing of olaparib. All patients will then undergo germline and somatic whole exome sequencing (WES) to assess iHRD status. Only those found to be iHRD+ will be used for the purpose of assessing the primary endpoint (i.e. best PSA response). Those patients that are LOH score-positive/iHRD-negative will be allowed to continue on treatment, however, and will be used in assessment of exploratory objectives. All patients will continue on androgen deprivation therapy (ADT) (i.e. surgical or medical castration) and should have a two-week washout from their most recent mCRPC therapy and weaned from steroids prior to enrolment.

PSA will be measured on day 1 of each treatment cycle. Radiographic assessment with bone and CT scans will occur every 12 weeks. The primary endpoint will be lowest on-treatment PSA and primary objective is to determine the PSA50 rate. Patients will be permitted to continue until disease progression by radiographic (per RECIST 1.1), PSA (per PCWG3 criteria) or clinical criteria (e.g. increasing pain), whichever comes first. Prior to completing 3 cycles of treatment, patients should not discontinue treatment for PSA progression alone. Patients will come off study at time of clinical, radiographic, or PSA progression. Secondary objectives will include assessment of radiographic PFS, PSA PFS, overall survival, and adverse events.

For an overview of the study design see Figure 1, Section 1.3. For details on treatments given during the study, see Section 5.5 Treatments Administered.

For details on what is included in the efficacy and safety endpoints, see Section 3 Objectives and Endpoints.

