6.8 Sample size determination

Based on the PROFOUND study, we estimate a response rate of 20% (H0) in patients with any HR mutations (e.g. BRCA2, ATM, CDK12, CHEK2, etc).² We will require a 50% (H1) response rate in iHRD positive patients to justify further development of this approach for selecting patients for olaparib treatment. Therefore, assuming we enroll 20 iHRD positive patients, this study would provide 87% power at a one-sided alpha of 0.03 to detect a 50% response rate compared to the null rate of 20%. Given that prior experience has shown that ~75% of patients with a positive LOH score will also have evidence of iHRD positivity, we will enroll a total of 30 patients to identify at least 22 iHRD positive subjects. This should allow for a drop out rate of 10% to ensure that at least 20 iHRD positive subjects are able to reach 12 weeks of treatment for the primary endpoint analysis.

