6.9 Statistical analyses

6.9.1 Efficacy analyses

Primary Objective

The primary objective is to determine the percentage of patients who are iHRD+ that achieve a PSA₅₀ response (i.e. $\geq 50\%$ decline in PSA from baseline). The lowest on treatment PSA will be defined as the lowest value following at least 12 weeks of treatment (i.e. the beginning of Cycle 4). The PSA₅₀ response rate will be calculated along with 90% confidence intervals (CI) using Wilson's method. PSA changes will be presented as waterfall plots per PCWG3 recommendations. If a patient drops out of the study prior to assessing best PSA response he will be considered as not having had a PSA₅₀ response.

ORR Response

For patients with measurable disease, ORR will be defined as a 30% decrease from baseline per RECIST 1.1 criteria at any time point. The percent of patients with ORR and 90% CI, calculated using Wilson's method, will be provided. Radiographic responses will be presented as waterfall plots.

rPFS, PSA PFS, OS

These endpoints are defined in section 3.5. The distributions of each endpoint will be estimated using the Kaplan-Meier method. Median times to event will be reported with 90% CIs using linear interpolation between steps of the survival curve.

Exploratory Objectives

Response rates and time to event endpoints as described above will be compared between patients who are iHRD+ and iHRD-. PSA and radiographic response rates including percentage and 90% CIs, calculated using Wilson's method, will be reported. Differences in response rates will be quantified using logistic regression with no additional adjustment. Time to event endpoints will be compared with log-rank tests.

If dropout is greater than anticipated, primary and secondary endpoint analyses will still be based on patients with 12 weeks of follow-up. However, the exploratory analysis will examine extreme scenarios in which endpoints for dropouts are imputed to minimize differences between iHRD+ and iHRD- patients.

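### The iHRD+ versus iHRD- response comparison rests on unadjusted logistic regression, which has no finite odds ratio if none of the 7 to 8 expected iHRD- men responds

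*Combined protocol and SAP*

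**What the plan says.** Section 6.9.1, under Exploratory Objectives, compares response between iHRD+ and iHRD- men. Each group's PSA and radiographic response rate is reported with a 90% Wilson interval. For the difference, the text says: "Differences in response rates will be quantified using logistic regression with no additional adjustment". It names no penalised or exact version and no rule for a group with zero responders. Time-to-event endpoints are compared between the same groups by log-rank tests.

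The group sizes follow from section 6.8, which expects that about "75% of patients with a positive LOH score will also have evidence of iHRD positivity" and states that "we will enroll a total of 30 patients to identify at least 22 iHRD positive subjects". Section 4.1 says that the LOH-positive, iHRD-negative men "will be allowed to continue on treatment, however, and will be used in assessment of exploratory objectives". They are the whole comparison group.

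**The concern.** With a single binary covariate, the maximum-likelihood log odds ratio is finite only if both groups contain at least one responder and one non-responder. A group of 7 or 8 men with a low response rate can easily contain no responder. Software then usually returns a very large coefficient with an enormous standard error, and its default Wald p-value is close to 1 however strongly the data separate the groups.

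At stake is the one named between-group method for response. The primary analysis estimates a rate in iHRD+ men alone, so it cannot show whether iHRD separates responders from non-responders. Exploratory objective 1 is where that question is put. If the stated method gives no usable odds ratio, a substitute would have to be chosen after the data are seen.

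**Working it through.** **1. The plan's own figure.** Section 6.8 sets "we estimate a response rate of 20% (H0) in patients with any HR mutations" against "We will require a 50% (H1) response rate in iHRD positive patients" and claims "87% power at a one-sided alpha of 0.03" with 20 iHRD+ men. An exact binomial rule of at least 8 responders in 20 gives:
- P(X ≥ 8 | 0.20) = 0.032
- P(X ≥ 8 | 0.50) = 0.868

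The stated figure reproduces. It concerns the primary analysis; the documents give no operating figure for the between-group comparison.

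**2. Size of the iHRD- group.** 30 × 0.75 = 22.5 iHRD+, leaving 30 × 0.25 = 7.5 iHRD-. So 7 or 8 men.

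**3. Probability of zero iHRD- responders.** This is (1 − p)^n. The documents give no value of p for LOH-positive, iHRD- men, so p is an assumption. The range below uses rates quoted for other groups, plus 30% as a sensitivity value.

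| Assumed p | Where the figure appears | n = 7 | n = 8 |
|---|---|---|---|
| 6% | Section 2.1, men without DNA-repair alterations | 0.94^7 = 65% | 0.94^8 = 61% |
| 10.5% | Section 2.1, ATM-mutated men, composite response | 0.895^7 = 46% | 0.895^8 = 41% |
| 20% | Section 6.8, null rate for HR-mutated men | 0.80^7 = 21% | 0.80^8 = 17% |
| 30% | Sensitivity value only | 0.70^7 = 8% | 0.70^8 = 6% |

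With an iHRD+ rate of 50%, the chance that all or none of the 22 to 23 iHRD+ men respond is under 0.001, so these are in effect the probabilities of no finite estimate. Treating the iHRD- count as Binomial(30, 0.25) gives 64%, 45% and 22% at 6%, 10.5% and 20%.

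Zero responders is more likely than not only when p is below 1 − 0.5^(1/7) = 9.4% for 7 men, or 1 − 0.5^(1/8) = 8.3% for 8.

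**4. Radiographic response.** Section 6.9.1 limits ORR to men with measurable disease, so the denominator is smaller. If only 4 iHRD- men were measurable (an assumption), the probability would be 0.94^4 = 78% at 6% and 0.80^4 = 41% at 20%.

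**5. What each method returns for 11/22 versus 0/8 (illustrative data).**
- Ordinary logistic regression, default output: log odds ratio 22.6, SE about 17,040, so z = 0.0013 and Wald p = 0.999.
- Likelihood-ratio test from the same model: log-likelihood −15.25 with the iHRD term (22 ln 0.5) and −19.71 without it (11 ln(11/30) + 19 ln(19/30)). Chi-square = 8.93, p = 0.003. The 90% profile lower bound for the odds ratio is 4.9; there is no finite upper bound.
- Fisher's exact test, two-sided: p = 0.014.
- Risk difference: 50 points. The Wilson 90% intervals are 33.5% to 66.5% for 11/22 and 0% to 25.3% for 0/8. Newcombe lower limit: 50 − √(16.5² + 25.3²) = 20. Upper limit: 50 + √(16.5² + 0²) = 67 after rounding (66.5).
- Firth-penalised odds ratio: here the same as adding 0.5 to each cell, (11.5 × 8.5)/(11.5 × 0.5) = 17.0, with 90% profile interval 2.4 to 723.

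**The case against.** A reader might infer that a failed model is the likely result. The documents do not support that. It would need a true iHRD- rate below about 8 to 9%, and no such rate is given. The 6% figure describes men without DNA-repair alterations in another trial, whereas every iHRD- man here is LOH-positive, a feature that section 4.2 links to response to PARP inhibition.

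Nor does the protocol's hypothesis predict zero responses among iHRD- men. It says that iHRD should find more men who may benefit, and section 6.9.1 foresees BRCA-mutant iHRD- patients. If one of 8 were BRCA-mutant and responded at the 83.3% quoted in section 2.1, with the other seven at 6%, the chance of zero responders would be 0.167 × 0.94^7 = 11%.

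It would also be too strong to say that logistic regression itself fails, or that this is the trial's only test of iHRD. The plan does not specify Wald inference, and step 5 shows that likelihood-ratio inference from the same model remains available. The log-rank tests also compare the groups, and the per-group Wilson intervals are valid at 0/7 or 0/8. The analysis is exploratory, with no alpha or decision rule attached.

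All of this stands and limits the importance of the point. What remains is that the only method named for the response difference has no provision for a zero cell that has an appreciable probability over much of the plausible range.

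**Conclusion.** The point holds as a cheap improvement. The chance that the planned odds ratio has no finite estimate runs from 6 to 8% at an assumed iHRD- rate of 30%, through 17 to 21% at 20%, to 61 to 65% at 6%. At any given rate it is higher for radiographic response, because fewer men are evaluable. These figures assume 7 or 8 iHRD- men and independent responses, and they depend on an iHRD- rate that the documents do not give. The reading that default Wald output would be reported is also an inference, since the plan says only that logistic regression will be used. The primary PSA50 analysis and its sample size are unaffected.

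**What to change.** In section 6.9.1, replace the logistic regression sentence. Quantify the iHRD+ versus iHRD- difference in response as a risk difference with a Newcombe 90% interval, which builds on the Wilson intervals already planned, together with Fisher's exact test. If an odds ratio is also wanted, specify Firth-penalised logistic regression with profile-likelihood intervals, or exact logistic regression.

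The cost is one sentence and standard software, with no change to enrolment, data collection or patient care. The drawbacks are small: Firth estimates shrink slightly towards the null, and Fisher's test is somewhat conservative.

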Based on the PROFOUND study, we estimate a response rate of 20% (H0) in patients with any HR mutations (e.g. BRCA2, ATM, CDK12, CHEK2, etc).² We will require a 50% (H1) response rate in iHRD positive patients to justify further development of this approach for selecting patients for olaparib treatment. Therefore, assuming we enroll 20 iHRD positive patients, this study would provide 87% power at a one-sided alpha of 0.03 to detect a 50% response rate compared to the null rate of 20%. Given that prior experience has shown that ~75% of patients with a positive LOH score will also have evidence of iHRD positivity, we will enroll a total of 30 patients to identify at least 22 iHRD positive subjects. This should allow for a drop out rate of 10% to ensure that at least 20 iHRD positive subjects are able to reach 12 weeks of treatment for the primary endpoint analysis.

[figure not shown]
The primary objective is to determine the percentage of patients who are iHRD+ that achieve a PSA₅₀ response (i.e. $\geq 50\%$ decline in PSA from baseline). The lowest on treatment PSA will be defined as the lowest value following at least 12 weeks of treatment (i.e. the beginning of Cycle 4). The PSA₅₀ response rate will be calculated along with 90% confidence intervals (CI). PSA changes will be presented as waterfall plots per PCWG3 recommendations. If a patient drops out

of the study prior to assessing best PSA response he will be considered as not having had a PSA50 response. However, an additional study subject will be enrolled to ensure an adequate number of subjects are available to estimate the PSA50 response rate.

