5.11.1 Procedures for discontinuation of study treatment

The investigator should instruct the patient to contact the site before or at the time if Study treatment is stopped. A patient that decides to discontinue Study treatment will always be asked about the reason(s) and the presence of any AEs. The date of last intake of Study treatment should be documented in the CRF (electronic or paper). All Study treatment should be returned by the patient at their next on-site study visit or unscheduled visit. Patients permanently discontinuing Study treatment should be given locally available standard of care therapy, at the discretion of the Investigator.

Any patient discontinuing investigational product should be seen post discontinuation for the evaluations and sample collections outlined in the study schedule.

After discontinuation of the study medication at any point in the study, all ongoing AEs or SAEs must be followed until resolution unless, in the Investigator's opinion the condition is unlikely to resolve due to the patients underlying disease, or the patient is lost to follow up (see Section 5.12) All new AEs and SAEs occurring during the 30 calendar days after the last dose of study medication must be reported (if SAEs, they must be reported within 24 hours as described in Section 6.4.2) and followed to resolution as above. Patients should be seen within 30 days after discontinuing study medication to collect and / or complete AE information. For guidance on reporting adverse events after the 30 day follow up period see Section 6.4.2.1.

Discontinuation of Study treatment, for any reason, does not impact on the patient's participation in the study. The patient should continue attending subsequent study visits and data collection should continue according to the study protocol. If the patient does not agree to continue in-person study visits, a modified follow-up must be arranged to ensure the collection of endpoints

and safety information. This could be a telephone contact with the patient, a contact with a relative or treating physician, or information from medical records. The approach taken should be recorded in the medical records. A patient that agrees to modified follow-up is not considered to have withdrawn consent or to have withdrawn from the study.

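### Section 6.9.1 gives two rules for early dropouts; the one for high dropout removes only PSA50 failures and inflates the primary response rate

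*Combined protocol and SAP*

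**What the plan says.** The Primary Objective paragraph of section 6.9.1 sets the first rule: "If a patient drops out of the study prior to assessing best PSA response he will be considered as not having had a" PSA50 response. He stays in the denominator as a failure. The synopsis (Statistical Methods) says the same and adds that "an additional study subject will be enrolled to ensure an adequate number of subjects are available to estimate" the rate. Section 6.9.1 does not mention this replacement.

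The second rule sits under Exploratory Objectives in section 6.9.1 but names the primary endpoint. If dropout is greater than anticipated, "primary and secondary endpoint analyses will still be based on patients with 12 weeks of follow-up". The sentence after it offers a safeguard, in that "the exploratory analysis will examine extreme scenarios in which endpoints for dropouts are imputed", but only for the iHRD+ versus iHRD- comparison.

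Two other statements bear on the denominator. The endpoint itself is restricted: "The lowest on treatment PSA will be defined as the lowest value following at least 12 weeks of treatment". Section 6.8 anticipates 10% dropout and sizes the trial so that "at least 20 iHRD positive subjects are able to reach 12 weeks of treatment for the primary endpoint analysis".

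**The concern.** The two rules give different denominators for the same endpoint, and no section ranks them. The difference has a direction. A man who leaves follow-up before week 12 has no PSA value that can count, so under the first rule he is always a failure. Under the second he disappears. With at least one responder and one such man, the second rule always gives the higher rate.

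The trial is judged on one proportion against a 20% reference, so an analyst could reach either conclusion from the same data and cite section 6.9.1 for both. On the literal wording, the more favourable rule comes in when dropout is high, which is when it changes the rate most. The exploratory imputation does not protect the primary result.

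The sentence also covers the secondary endpoints. Read literally, it drops deaths before week 12 from overall survival, although section 5.12 asks for survival status on all patients in the full analysis set. For rPFS and PSA PFS the effect depends on who is still followed, and the documents disagree on that. Section 4.1 says "Patients will come off study at time of clinical, radiographic, or PSA progression", while section 5.11.1 says "Discontinuation of Study treatment, for any reason, does not impact on the" patient's participation and continues visits.

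**Working it through.** **Inputs.** From section 6.8: null rate 20%, alternative 50%, 20 evaluable iHRD+ men, one-sided alpha 0.03, power 87%, at least 22 iHRD+ enrolled, 10% dropout. From section 6.9.1: 90% Wilson interval. Assumed: dropout of 20% and 30%, and the responder counts used as examples.

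**1. The plan's own figure.** No responder cutoff is stated. Requiring at least 8 of 20:
- alpha = P(X ≥ 8), X ~ Bin(20, 0.20), = 0.032
- power = P(X ≥ 8), X ~ Bin(20, 0.50), = 0.868

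These match 0.03 and 87%. The cutoff of 8/20 is therefore inferred, and an exact level of at most 0.0325 reproduces it.

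**2. Size of the shift in the rate.** Excluding d dropouts multiplies the observed rate by 22/(22 − d): 1.10 for d = 2, 1.22 for d = 4, 1.38 for d = 6.

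**3. One dataset, two answers.** Take 22 men with 4 early dropouts.

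| Responders | Dropouts as failures | 12-week men only |
|---|---|---|
| 8 | 8/22 = 36.4%, exact p = 0.056, Wilson lower bound 21.9% | 8/18 = 44.4%, exact p = 0.016, Wilson lower bound 27.2% |
| 7 | 7/22 = 31.8%, Wilson lower bound 18.3% | 7/18 = 38.9%, Wilson lower bound 22.7% |

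Eight responders change the conclusion under the exact test but not under Wilson. Seven change it under Wilson.

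**4. False success.** Suppose the true rate with dropouts as failures is 20%. With dropout probability d, the number with 12 weeks of follow-up is m ~ Bin(22, 1 − d), and their response rate is 0.20/(1 − d): 25.0% at d = 20% and 28.6% at d = 30%. For each m, take the smallest count that succeeds for that denominator, find the chance of reaching it, and average over m. In the triggered version the denominator is m only when more than 2 of 22 drop out, and otherwise stays at 22.

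| Success criterion | All 22 kept | Completers, d = 20% | Completers, d = 30% | Triggered, d = 20% | Triggered, d = 30% |
|---|---|---|---|---|---|
| Exact p ≤ 0.0325 | 2.0% | 6.5% | 10.9% | 5.8% | 10.7% |
| Wilson 90% lower bound > 20% | 5.6% | 15.5% | 24.0% | 14.3% | 23.7% |

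**5. Overall survival, upper illustration only.** Assume exponential survival with the 17.5-month median quoted in section 2.1 for the combined cohorts of the phase III olaparib trial. Twelve weeks is 2.76 months.
- P(death before week 12) = 1 − 0.5^(2.76/17.5) = 0.104
- Median from first dose after excluding those deaths = 2.76 + 17.5 = 20.3 months

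Entry requires a life expectancy of at least 16 weeks, so the real shift should be smaller.

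**The case against.** **No decision rule is declared.** Section 6.9.1 specifies a rate with a Wilson interval. The exact test is inferred from section 6.8, and 8 responders do not change the conclusion under Wilson. If section 6.8 is read as requiring an observed 50%, both 36.4% and 44.4% fall short. This stands as a limit on the example. The reported rate still moves under any criterion, and the change of conclusion appears under Wilson with 7 responders.

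**The null may refer to completers.** Section 6.8 does not give the denominator behind the 20%. If it is the rate among men reaching 12 weeks, completers-only false success is about 2.0% at 20% dropout and 1.9% at 30%, so there is no inflation. This is correct. The error-rate figures depend on the all-patient reading, which is the one that fits the non-responder rule.

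**The contrast is partly discreteness, and dropout may be low.** The 2.0% baseline comes from 9/22, whereas the plan's design point is 3.2%. At the planned 10% dropout with the trigger, false success is 3.0%. Both points are fair. The sentence, however, was written for dropout above plan.

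**Few men may be removed.** The wording is follow-up, not treatment. Men who stop the drug but stay under observation are kept, and the protocol discourages stopping for PSA progression alone before three cycles. The number removed is therefore unknown, because sections 4.1 and 5.11.1 disagree on who stays in follow-up.

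**The rule may not be a switch.** The word "still" in the sentence, and section 6.8, suggest that the 12-week set was intended throughout. In that case the conflict with the non-responder rule exists at every dropout level.

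**Conclusion.** The concern holds. Two current sentences in the same section prescribe different primary denominators, and the 12-week rule can only raise PSA50, because the men it removes cannot be responders under the plan's own endpoint definition. That direction needs no assumption beyond at least one responder and one excluded early leaver. The size does: the pass/fail example uses the inferred exact rule, and the roughly three- to five-fold rise in false success (2.0% to 6.5% and 10.9%) uses an all-patient null of 20% with assumed dropout of 20% and 30%.

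Replacement as described in the synopsis does not settle the matter. It is compatible with counting failures only if the replaced man stays in the denominator, and the plan does not say so. The effect on overall survival is in the same direction but only loosely bounded. The effect on rPFS and PSA PFS cannot be sized from the documents and is probably smaller, since the first scan is at week 12. This must be fixed before analysis, because a written rule would bias the primary result.

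**What to change.** - Delete the 12-weeks-of-follow-up sentence for primary and secondary endpoints.
- Define the primary set as all iHRD+ patients who took at least one dose of olaparib, with no qualifying PSA counted as non-response at any level of dropout.
- State in sections 1.2 and 6.9.1 that a replacement patient adds to this denominator and does not substitute for the man replaced.
- Analyse rPFS, PSA PFS and OS from first dose in all treated iHRD+ patients.
- Keep the 12-week completers as a labelled sensitivity analysis.
- Restate section 6.8 for the full denominator, with the success criterion and the denominator behind the 20% made explicit.

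The cost is wording, a lower reported rate and less power. With 22 patients the rule becomes at least 9/22, with alpha P(X ≥ 9 | 22, 0.20) = 0.020. Power is P(X ≥ 9 | 22, 0.50) = 86% if 50% is the rate including dropouts. If 50% is the rate among completers and 10% drop out, the all-patient rate is 0.50 × 0.90 = 45% and power is 72%, against the stated 87%. If 72% is too low, the sample size has to be revisited.

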5.1 Inclusion criteria

Patients are eligible to be included in the study only if all of the following inclusion criteria and none of the exclusion criteria apply:

1. Capable of giving signed informed consent which includes compliance with the requirements and restrictions listed in the informed consent form (ICF) and in this protocol.
2. Subject must be \geq 18 years of age at the time of signing the informed consent form.
3. Individuals who have documented histologically confirmed adenocarcinoma of the prostate.
4. Subject must have evidence of castration resistant prostate cancer as evidenced by PSA progression (per Prostate Cancer Working Group 3 [PCWG3] criteria) and a castrate serum testosterone level (i.e. \leq 50 mg/dL)¹.
5. PSA must be at least 2 ng/mL and rising on two successive measurements at least two weeks apart.
6. At least one lesion (measurable and/or non-measurable) that can be accurately assessed at baseline by CT scan, MRI, or PET and is suitable for repeated assessment.
7. Must have progressed on abiraterone and/or a second-generation AR antagonist (i.e. enzalutamide, apalutamide, or darolutamide). If these were given in the hormone sensitive setting, patients must also have progressed on at least one prior approved therapy for CRPC.
8. Must have archival tissue available or be willing to undergo metastatic biopsy in order to perform next-generation DNA sequencing and undergo whole exome sequencing.
9. Patient must have a positive LOH score on prior UW OncoPlex testing

10. Patients must have normal organ and bone marrow function measured within 28 days prior to administration of study treatment as defined below:

- Hemoglobin ≥ 10.0 g/dL with no blood transfusion in the past 28 days
- Absolute neutrophil count (ANC) $\geq 1.5 \times 10^9$ /L
- Platelet count $\geq 100 \times 10^9$ /L
- Total bilirubin $\leq 1.5 \times$ institutional upper limit of normal (ULN)
- Aspartate aminotransferase (AST) (Serum Glutamic Oxaloacetic Transaminase (SGOT)) / Alanine aminotransferase (ALT) (Serum Glutamic Pyruvate Transaminase (SGPT)) $\leq 2.5 \times$ institutional upper limit of normal unless liver metastases are present in which case they must be ≤ 5 x ULN
- Patients must have creatinine clearance estimated of ≥ 51 mL/min using the Cockcroft-Gault equation or based on a 24 hour urine test:

$$\text{Estimated creatinine clearance} = \frac{(140 - \text{age [years]}) \times \text{weight (kg)}}{\text{serum creatinine (mg/dL)} \times 72}$$

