We will additionally be looking at association between response rate and different predictors of homologous recombination deficiency including large scale state-transition (LST) score, COSMIC signature 3/8, and presence of underlying HR mutation. We will report the presence of underlying HR mutations in both the iHRD(+) and iHRD(-) groups. Depending on the final makeup of the study population, we will report PSA and radiographic response rates among various subsets which may include iHRD(+) and *BRCA* mutant iHRD(-) patients. We will also use the results of this trial to optimize iHRD classification framework and develop a clinical pipeline for calling iHRD from targeted exome panels. We will also describe the results of transcript profiling studies from tumor biopsies and compare pre and post treatment profiles.

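### Does the plan need a committed response estimate by BRCA/HR mutation status within iHRD+ patients, because the pooled PSA50 rate cannot show value beyond mutation testing?

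*Combined protocol and SAP*

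**What the plan says.** Section 6.8 sets the null from the PROfound study: "we estimate a response rate of 20% (H0) in patients with any HR mutations (e.g. BRCA2, ATM, CDK12, CHEK2, etc"). The target is tied to a development decision: "We will require a 50% (H1) response rate in iHRD positive patients to justify further development of this approach". The stated design is 20 iHRD+ patients, and "this study would provide 87% power at a one-sided alpha of 0.03 to detect a 50% response rate".

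The molecular entry condition in Section 5.1 is "Patient must have a positive LOH score on prior UW OncoPlex testing". BRCA status is neither required nor excluded.

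On mutation status, Section 6.9.1 (Exploratory Objectives) plans three things:

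- an association analysis, "looking at association between response rate and different predictors of homologous recombination deficiency", with presence of an HR mutation among the predictors;
- a tabulation of mutation carriers, "We will report the presence of underlying HR mutations in both the iHRD(+) and iHRD(-) groups", which concerns frequency and not response;
- subset response rates under a condition, "Depending on the final makeup of the study population, we will report PSA and radiographic response rates among various subsets which may include"; the examples named there are the iHRD+ group and BRCA-mutant iHRD- patients.

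Section 3.3 also lists response and PFS by specific HR gene, in a list introduced as examples. Radiographic response is limited by evaluability: "For patients with measurable disease, ORR will be defined as a 30% decrease from baseline per RECIST 1.1 criteria".

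**The concern.** The hypothesis in Section 2.1 is that iHRD will identify more men likely to benefit from PARP inhibition, including the 11-12% of mCRPC patients who carry no HR-gene mutation and are otherwise left out of such trials. The same section reports that response depends heavily on the gene: 83.3% with BRCA1/2 alterations, 10.5% with ATM, 0% with CDK12 and, in a different trial, 6% without DNA-repair alterations. A pooled iHRD+ rate therefore moves with the share of BRCA-altered men in the sample. If most responders carry BRCA alterations, the trial could meet its target and say little about men whom mutation testing would miss.

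The estimate that speaks to this is response within iHRD+ split by mutation status, and the plan never firmly promises it. The planned association with HR mutation is not confined to iHRD+, so its non-mutated group can mix iHRD+ and iHRD- men. The second commitment is mutation frequency, not response. The third is conditional twice over. In an open-label trial, subsets settled once the makeup is known can look selected. The HR mutation predictor in Section 6.9.1 also has no gene list and no rule on bi-allelic versus any alteration.

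**Working it through.** **1. The plan's own figure.** Inputs from Section 6.8: n = 20, null 0.20, target 0.50. No cut-off is stated, so it is inferred from X ~ Bin(20, p) with success if X ≥ r.

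| r | P(X ≥ r), p = 0.20 | P(X ≥ r), p = 0.50 |
|---|---|---|
| 7 | 0.087 | 0.942 |
| 8 | 0.032 | 0.868 |
| 9 | 0.010 | 0.748 |

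Only r = 8 gives both 0.03 and 87%. The design is correct as stated.

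**2. How often a success could be BRCA-driven.** Let k of the 20 be BRCA-altered with response rate b, and let the other 20 − k respond at rate q. Then X = Bin(k, b) + Bin(20 − k, q), and P(X ≥ 8) follows by exact convolution.

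- b = 0.833 is the Section 2.1 figure. It is a PSA-or-RECIST composite, so it only stands in for PSA50.
- b = 0.60 is an assumed lower PSA50 rate.
- q = 0.06 is the Section 2.1 rate without alterations; q = 0.10 is close to the ATM figure. Both describe a signature that adds nothing outside BRCA.
- k is unknown. Figure 3 implies that 107 − 65 = 42 of 107 iHRD+ tumors (39%, about 8 of 20) had bi-allelic loss in one of four genes. That is a different sample and includes ATM and PALB2, so it is illustrative.

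| k of 20 | b = 0.833, q = 0.06 to 0.10 | b = 0.60, q = 0.06 to 0.10 |
|---|---|---|
| 4 | 1-4% | under 2% |
| 6 | 9-21% | 2-7% |
| 8 | 47-60% | 11-19% |
| 10 | 85-89% | 30-39% |

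If an observed 10 of 20 (the 50% target itself) were required, then at b = 0.833 the chance is 5-13% with k = 8 and 35-46% with k = 10. The possibility is real, and its size runs from negligible to high over a range the documents do not narrow. Excluding prior PARP-inhibitor treatment (Section 5.2), when olaparib is already approved for HRR-mutated disease (Section 2.1), could lower k.

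**3. What the uncommitted table would show.** With k = 8 and b = 0.833, 93% (q = 0.06) or 82% (q = 0.10) of pooled successes would have at most 2 responders among the 12 others. The pattern would be visible in the counts. The 90% Wilson intervals, the method already set in Section 6.9.1, are:

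| Responders / n | 90% CI |
|---|---|
| 1/12 | 2-30% |
| 2/12 | 6-40% |
| 3/12 | 11-49% |
| 6/12 | 29-71% |
| 1/16 | 1-24% |
| 8/16 | 31-69% |

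The interval for 2/12 overlaps that for 6/12. Only clear extremes separate. Radiographic groups would be smaller still, since Section 4.2 notes that many patients have mainly bone disease.

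**4. What the pooled test claims.** Section 4.2 describes the trial as giving an initial estimate of activity in iHRD+ disease. Section 6.8 uses the result to decide on further development. Neither says that success establishes benefit beyond BRCA testing. Against a null taken from men with any HR mutation, the pooled test addresses whether iHRD enriches for responders, which is part of the hypothesis.

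**The case for a change.** The best argument for a change is that finding responders without an HR mutation is a stated purpose, that the one estimate bearing on it is left to discretion, and that committing to it costs a descriptive table from sequencing already planned. The factual part stands: no sentence promises response by mutation status within iHRD+, and the HR mutation variable lacks a definition. The 20% null is also historical and not matched on BRCA share.

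Three things weaken the argument. First, the ingredients are already planned or listed: response by HR gene, association of response with HR mutation, mutation status in both iHRD groups, and conditional subset rates. With mutation status recorded in the iHRD+ group and PSA response known for each patient, the cross-table is the natural next step, and making subsets conditional is defensible when composition is unknown and n is about 20.

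Second, a tighter rule carries its own cost. Declaring all other subsets post hoc would downgrade the gene-level analyses that Section 3.3 lists, and limiting BRCA-mutant iHRD- patients to counts would remove rates that Section 6.9.1 now allows. Reading success beside men without a BRCA1/2 alteration would also miss the target group, since that complement includes ATM- and CDK12-mutated men while the hypothesis concerns men with no HR-gene mutation.

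Third, the open-ended gene list in Section 6.8 describes the historical population behind the null. It does not define this trial's analysis groups, so it is not evidence of loose subgroup definitions.

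**Conclusion.** No change is needed. The primary test, sample size, error rates and the conclusion they support are sound as written. A pooled success should be read as an activity signal in iHRD+ disease, and not on its own as proof of benefit in mutation-negative men. What is missing is a firm commitment to one exploratory cross-table, a gap analysts can sensibly fill from planned data with Wilson intervals. A gene list and alteration definition fixed before analysis would be good practice for that table, as an optional reporting refinement.

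The chance of a BRCA-driven success at 8 of 20 or more runs from about 1-4% (4 BRCA-altered of 20) through 47-60% (8 of 20) to 85-89% (10 of 20). This assumes the inferred cut-off, 83.3% response in BRCA-altered men and 6-10% in the rest, with rates borrowed from other trials and partly from a composite endpoint. At an assumed 60% BRCA response the same shares give under 2%, 11-19% and 30-39%. The BRCA share is not in the documents, so none of these is a forecast. The split would be shown by the table whether or not it is promised in advance, and at about 12 mutation-negative patients it could separate only extreme results.
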